Samples will be provided in two 2-week shipments, with sufficient number of tanks to last ~4 weeks. We will send 2nd shipment only after request for more product is initiated by participant, either through response to diary question, call to our 1-800 number, or return of a mailback card sent along with 1st shipment. Flavors for 2nd shipment will be participant-driven. No more than 30 tanks will be sent to any one participant, no more than 20 for first shipment (slightly more than half of sampling period, to account for lag time after 2nd mailing) and 10 for second shipment. Each shipment will contain instructions not to allow anyone else to use the product, to store in a location out of reach of minors, and how to safely charge/clean product, per FDA guidelines. Based on a recent experience from [name] and also through personal communications with both he and [name], we anticipate that ~25% of the sample will use daily; 50% will use for about 2 weeks, and 25% will use less than that; these are all conservative estimates, as we do not want to artificially suppress uptake through insufficient sampling. Driven largely by our prior studies on product sampling, we believe this 4-wk period allows for a sufficient period of acclimation, in which smokers determine if they like it, and how to use it to manage cravings. This period also allows sufficient time to observe naturalistic changes in cigarette smoking, dynamic and concurrent in time with uptake of e-cigarette use. Smokers will not be asked to return product, but we will assess sustained and/or intermittent use over extended duration (6 months). Our group has a strong record of this sampling “intervention,” in which we give smokers the opportunity to try new products over a short period, testing their impact both during and beyond the sampling period (see above).

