1.3 Potential Risks

The research protocol calls for non-treatment seeking smokers to either use e-cigarettes or not. Use of e-cigarettes is entirely self-chosen, since this is one outcome, rather than prescribed. E-cigarettes are no more harmful than conventional cigarettes, and various studies suggest that they may offer reduced harm. Questionnaires and interviews are all non-invasive and involve minimal risk to study participants. Potential risks are as follows:

- 1) risk of using e-cigarettes
- 2) concurrent use of e-cigarettes & smoking
- 3) potential for undermining cessation
- 4) non-smokers in the home (children) experimenting with e-cigarettes
- 5) loss of confidentiality

1.3.1 E-Cigarettes E-Cigarettes are not combusted, and therefore levels of carcinogens are markedly reduced, if not eliminated, comparable to trace levels seen in nicotine replacement products (26). Nicotine liquid is based on a solution containing propylene glycol, which some suggest may be harmful. Propylene glycol is an FDA approved food additive, but with uncertain effects upon inhalation. The detailed NIDA-guided DSMP (Section 4 below) presents data on tobacco-specific nitrosamines (TSNAs), within both e-cigarettes and their vapor.

As for adverse events, the majority of e-cigarette studies are based within on-line surveys. We report here on three moderate to large such surveys, 2 recently published (2013) and one from 2011 but is the largest survey to date. In the first (32), three side effects were reported by >20% of respondents: headaches (21%), cough

(27%), and increased phlegm (25%). In the second (33), the most common negative effect of e-cigarette use was throat and mouth irritation, and fewer than 3% “reported a high level of side effects.” Finally, the largest online survey to date (56) did not fully assess adverse events, but reported that 26% of e-cigarette users reported burning in throat. In a cross-over study of 40 smokers given e-cigarette for four days (14), the four most common adverse events (within highest dosage group) were mouth/throat irritation (38%), nausea (29%), vertigo (21%) and headache (22%). All other adverse events were rare (<5%). There have also been a small number of reports to the FDA of people using e-cigarettes and experiencing seizures, with most reports involving youth or young adult users. These are rare, but we will inform participants of this risk and monitor.

[figure not shown]

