b) The research staff will report any unexpected AEs or any scores of "severe" on the side-effect symptom rating form or any FDA-defined serious AEs to the PI within 24 hrs so that the PI can decide on the appropriate action. All unexpected AEs will be monitored while they are active to determine if treatment is needed. Since a maximum three week supply of e-cigarettes, adverse events will be rare. Nonetheless, they will be coded on a weekly basis using the FDA's COSTART rules (142) and entered into a database. For each weekly study meeting, the research assistants will prepare a summary of all AEs, including their severity, whether they occurred during smoking or abstinence, caused a dropout, required treatment and presumed relation to drug intake. The PI will review this at the weekly study meeting (or before if more urgent). At the weekly meeting (or before if urgent), research assistants will report any premonitory symptoms of emergence of a mental disorder such as depression or alcohol dependence. [name], a board-certified psychiatrist, [name], a radiation oncologist (both with expertise in nicotine dependence and treatment) will be available for medical supervision. Any study-related SAE will be reported to the DSMB immediately, which may convene a special meeting. Aggregate summary of all AEs will be provided quarterly to the DMSB and at each regularly scheduled DSMB meeting.

14. Conflicts of Interest

The Medical University of South Carolina is fully compliant with federal laws in reporting of conflicts of interest. All key personnel listed within this application have complied with this policy. Any conflicts of interest will be acknowledged in any publications or conference proceedings.

15. Potential risks and benefits to participants

The research protocol calls for non-treatment seeking smokers to either use e-cigarettes or not. Use of e-cigarettes is entirely self-chosen, since this is one outcome, rather than prescribed. E-cigarettes are no more harmful than conventional cigarettes, and various studies suggest that they may offer reduced harm. Questionnaires and interviews are all non-invasive and involve minimal risk to study participants. Potential risks are as follows:

- 1) risk of using e-cigarettes
- 2) concurrent use of e-cigarettes & smoking
- 3) potential for undermining cessation
- 4) non-smokers in the home (children) experimenting with e-cigarettes
- 5) loss of confidentiality

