15.1 E-Cigarettes Tables I and II below provide, respectively, levels of tobacco-specific nitrosamines across a number of nicotine delivery devices, and levels of toxicants within cigarette smoke and e-cigarette vapor. Table I data show that TSNAs within e-cigarettes are much lower than tobacco products, including low-nitrosamine smokeless tobacco. Table II shows that e-cigarette vapor includes significantly lower levels of a number of toxicants as compared to cigarette smoke.

Table I: Tobacco-Specific Nitrosamines within Nicotine-Delivery Products

Tobacco-Specific Nitrosamines					
Product	NNN	NNK	NAT	NAB	Total
Nicorette gum	2.00	ND	ND	ND	2.00
Nicoderm CQ patch	ND	8.00	ND	ND	8.00
E-cigarettes	3.87	1.46	2.16	0.69	8.18
Swedish Snus	980	180	790	60	2010
Marlboro (Ultra-light)	2900	750	1100	58	4808
Marlboro (full)	2900	960	2300	100	6260

Source: Cahn 2010

Among human studies, the majority of e-cigarette studies are based within on-line surveys. We report here on three moderate to large such surveys, 2 recently published (2013) and one from 2011 but is the largest survey to date. In the first (32), three side effects were reported by >20% of respondents: headaches (21%), cough (27%), and increased phlegm (25%). In the second (33), the most common negative effect of e-cigarette use was throat and mouth irritation, and fewer than 3% “reported a high level of side effects.” Finally, the largest online survey to date (56) did not fully assess adverse events, but reported that 26% of e-cigarette users reported burning in throat. In a cross-over study of 40 smokers given e-cigarette for four days (14), the four most common adverse events (within highest dosage group) were mouth/throat irritation (38%), nausea (29%), vertigo (21%) and headache (22%). All other adverse events were rare (<5%).

Table II: Toxicant Levels within E-cigarette Vapor vs. Cigarette Smoke

Toxic compound	Conventional cigarette [μg in mainstream smoke]	Electronic cigarette [μg per 15 puffs]	Average ratio (conventional vs. electronic cigarette)
Formaldehyde	0.85-10	0.20-5.61	2
Acetaldehyde	52-140	0.11-1.36	130

Acrolein	4.6-14	0.07-4.19	4
Toluene	6.4-9.0	0.02-0.63	23
NNN	0.012-0.37	0.00008-0.00043	145
NNK	0.009-0.08	0.00011-0.00283	30
Cd	0.03-0.35	0.001-0.022	16
Ni	0.003-0.60	0.011-0.029	15
Source: Goniewicz 2014			

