15.2 Concurrent use of e-cigarettes and smoking

If smokers engage in dual use, the major concern will be intake of nicotine, and too much of it. Symptoms of nicotine intoxication include nausea, dizziness, headache, and stomachache (140). In our two prior studies wherein participants who used nicotine gum/lozenge and smoked concurrently, there was no evidence of nicotine intoxication (75, 76), nor have we seen serious adverse events in our current e-cigarette studies. We recently completed a literature review (141) that showed combined NRT, as well as concurrent use of NRT and smoking, were both safe.

15.3 Undermining Cessation Another potential risk is that the sampling intervention will decrease rather than increase future cessation. However, the limited data available suggest this is unlikely (32, 44, 45, 56).

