This study is not without benefit to individual participants. However, this is not a treatment trial, and will not be advertised as such. We assess at screening for interest in cessation support. All comers will be accepted, but smokers actively seeking cessation support, or currently using cessation medication at baseline will be excluded. At all contacts, we will assess motivation to quit and uniformly offer referral information to state quitlines. Such transitions to cessation support are included as study outcomes. Two-thirds of the participants in the trial will receive samples of e-cigarettes, which most evidence to date suggests is a) safer than conventional cigarettes, and b) possibly related to quitting.

16. Collection, reporting and management of AEs and SAEs

Adverse events will be tracked and rated as mild, moderate or severe by the patient and rated as related to e-cigarettes by the research assistant using guidelines. We will determine if any adverse events result in dropouts or are serious according to FDA guidelines. A DSMB will assist in determining if the rate or severity of adverse events exceeds expectations.

The research staff will report any unexpected AEs or any scores of "severe" on the side-effect symptom rating form or any FDA-defined serious AEs to the PI within 24 hrs so that the PI can decide on the appropriate action. All unexpected AEs will be monitored while they are active to determine if treatment is needed. Since the e-cigarette sampling period is for a few weeks only, adverse events will be rare. Nonetheless, they will be coded on a weekly basis using the FDA's COSTART rules and entered into a database. For each weekly study meeting, the research assistants will prepare a summary of all AEs, including their severity, whether they occurred during smoking or abstinence, caused a dropout, required treatment and presumed relation to drug intake. The PI will review this at the weekly study meeting (or before if more urgent). At the weekly meeting (or before if urgent), research assistants will report any premonitory symptoms of emergence of a mental disorder such as depression or alcohol dependence. [name], a board-certified psychiatrist, and [name], a radiation oncologist, will be available for on-site medical supervision.

17. Plans for Interim Analyses of efficacy data

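### The planned adverse-event summary classes events by smoking or abstinence, with no item for e-cigarette or dual use at onset, and the safety outputs specify no breakdown by arm or by use

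*Combined protocol and SAP*

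**What the plan says.** DSMP section 13 b) describes two things. Events are handled so that "they will be coded on a weekly basis using the FDA's COSTART rules (142) and entered into a database", and a weekly summary is prepared for the principal investigator covering all events, "including their severity, whether they occurred during smoking or abstinence, caused a dropout, required treatment and presumed relation to drug intake". Section 16 repeats that list and adds that events are "rated as related to e-cigarettes by the research assistant using guidelines".

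Section 15.2 explains why concurrent use matters: "If smokers engage in dual use, the major concern will be intake of nicotine, and too much of it". Section 2.2.2 lists adverse-event tracking at every study contact among the protections against that risk.

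The analysis is set out in one place, under Ancillary Analyses. It gives the incidence of adverse events with a 95% confidence interval and a chi-square test of whether the serious-event rate exceeds 5%. The monitoring board receives an aggregate summary quarterly (section 13 b) and a report with adverse events in aggregate plus a listing of serious events (section 20).

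On seizures, section 1.3.1 says: "These are rare, but we will inform participants of this risk and monitor". It also describes respiratory illness in users of e-devices and undertakes to keep monitoring participants' health. DSMP section 15.1 repeats the survey and cross-over data from 1.3.1 but mentions neither.

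**The concern.** Classing an event by smoking or abstinence suits a quitting trial. Here the randomized exposure is an e-cigarette sample, and the second listed risk is using it alongside cigarettes. The one exposure state named for an event does not identify that combination.

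Arm alone is a weak substitute for use at onset, because use is voluntary and expected to be uneven. The section on the e-cigarette group anticipates about a quarter using daily, while "50% will use for about 2 weeks, and 25% will use less than that". An event in that arm may fall on a day with no vaping, and controls may vape on their own account.

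What is at stake is how informative the safety result is. If the plan is followed as written, the report would be a pooled incidence that does not separate vaping, dual use, smoking alone and neither.

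**Working it through.** This is mainly a comparison of what the plan records with what it reports. One small calculation shows how little the stated item separates.

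**1. What the item distinguishes.** At onset a participant is in one of four states. The stated item reduces these to two:
- Smoking: cigarettes only, or cigarettes and e-cigarettes.
- Abstinence: e-cigarettes only, or neither. Even this is unsettled, since the Hyp 3 analyses are to be repeated with abstinence defined to include e-cigarettes.

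**2. How many people it separates at six months, on planning values.** Inputs are 440 and 220 participants (Design Overview), abstinence of 16% and 8% (Sample Size & Power), and 25% of the e-cigarette group still using at least some at final follow-up (Hyp 1a).
- In the smoking class: 440 × (1 − 0.16) + 220 × (1 − 0.08) = 369.6 + 202.4 = 572 of 660, or 86.7%.
- E-cigarette users in the e-cigarette arm: 440 × 0.25 = 110. Abstainers in that arm: 440 × 0.16 = 70.4.
- If every abstainer vapes, dual users number 110 − 70.4 = 39.6. If no abstainer vapes, they number 110.
- Dual users are then 39.6/572 = 6.9% to 110/572 = 19.2% of the smoking class, and the item does not set them apart.

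These figures count participants, not events. They assume that the planning values hold, follow-up is complete and no control vapes.

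**3. What else could supply the exposure.**
- Diaries: daily for 28 days in both arms, covering cigarettes and e-cigarettes. No adverse-event item is listed among their contents, and the weekly summary names no onset date. Joining an event to a diary day is possible but not provided for.
- Phone assessments: days 10, 17 and 24, then months 1, 3 and 6. These give duration, quantity and frequency of e-cigarette use, from which dual-use patterns can be derived. After month 1 the gaps are about two and three months, too wide to place use at onset closely.
- Relatedness: rated by the research assistant in an unblinded trial without placebo. It is a judgement about cause and does not record use.
- Randomized arm: known for everyone.

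**4. What the outputs use.** None of these sources appears in a stated safety output. Ancillary Analyses names neither arm nor use. Section 20 asks for enrolment in aggregate and split by gender and race, but for adverse events in aggregate only, plus the serious-event listing. Section 21 ties quitting to the e-cigarette group but states no arm for adverse events.

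**5. The two risk texts.** Section 1.3.1 covers survey data, the cross-over study, seizures and respiratory illness. DSMP section 15.1 covers the first two only.

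**The case against.** The strongest reply is that the exposure data exist. Both arms report cigarette and e-cigarette use by diary and phone, events are asked about at the same contacts, events are rated for relation to e-cigarettes, and there is a randomized control arm. This stands. A reader might infer that the trial cannot show whether events follow vaping or dual use. The documents do not support that: linkage is fairly fine during the diary period and coarser afterwards, but not absent.

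Second, the quoted list describes a weekly meeting summary and is introduced as a set of inclusions. The fields of the adverse-event database are not listed and the symptom rating form is not reproduced. This also stands. It cannot be said that those instruments lack a vaping item, or items for seizure and respiratory symptoms.

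Third, the mismatch between the risk texts has limits. Section 21 commits to real-time updates to the board on vaping illness. Severe or serious events go to the principal investigator whichever list staff consult. Nor does section 15 as a whole take a milder view of harm, since its general statement comparing e-cigarettes with cigarettes also appears in section 1.3. What remains is the omission in 15.1.

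Fourth, the major concern named in section 15.2 is excess nicotine under dual use, and section 2.2.2 relies on more than event tracking. That narrows the point but leaves it standing, because whether both products were in use at onset is what one would want to know about such an event.

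**Conclusion.** The point holds as one of classification and pre-specification. The stated event summary does not separate the trial's own exposure, and the stated outputs use neither the arms nor the use data that the trial collects. Following the plan as written gives a less informative safety result at almost no saving.

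The size is modest. No endpoint, power calculation or error rate changes. On planning values, the smoking class at six months holds about 87% of participants and merges roughly 40 to 110 dual users with the rest. It is tempting to add a figure for how far a product effect would be diluted over six months. That would need assumed event rates and use days that the documents do not give, and it would measure the length of follow-up, not this classification.

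The conclusion assumes that the weekly list reflects what is recorded at onset. If the database or symptom form already captures e-cigarette use at onset, only the text and the table need changing.

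**What to change.** 1. In DSMP sections 13 b) and 16, replace the smoking-or-abstinence item with cigarette and e-cigarette use in a stated short window before onset (for example 24 hours), in four classes: cigarettes only, e-cigarettes only, both, neither. Record it in both arms, with the onset date. Events already reported can be classed from diary or call data, marked as such.

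2. Under Ancillary Analyses, add one descriptive adverse-event table by randomized arm, by use class, and by period (the 4-week sampling period versus afterwards). Give denominators, since the arms are 2:1. State that only the split by arm is a randomized comparison, because use is self-chosen. Define the period boundary explicitly: section 13 b) refers to a three-week supply and the design summary to four weeks, and these passages must be reconciled.

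3. Reconcile DSMP section 15.1 with section 1.3.1 on seizures and acute respiratory illness, so that staff and the board work from one risk description.

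The cost is one changed item, an onset date if not already held, one extra table and some text editing. Calls become slightly longer when an event is reported, and earlier events will be classed less precisely, especially those after day 28.

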15.2 Concurrent use of e-cigarettes and smoking

If smokers engage in dual use, the major concern will be intake of nicotine, and too much of it. Symptoms of nicotine intoxication include nausea, dizziness, headache, and stomachache (140). In our two prior studies wherein participants who used nicotine gum/lozenge and smoked concurrently, there was no evidence of nicotine intoxication (75, 76), nor have we seen serious adverse events in our current e-cigarette studies. We recently completed a literature review (141) that showed combined NRT, as well as concurrent use of NRT and smoking, were both safe.

15.3 Undermining Cessation Another potential risk is that the sampling intervention will decrease rather than increase future cessation. However, the limited data available suggest this is unlikely (32, 44, 45, 56).

15.4 Use of E-cigarettes among non-participants and non-smokers, including children

Whenever a product is given to a smoker to take home and use, there is potential that the product will be used by someone else, inclusive of non-smokers and even children. In our ongoing snus trial in which we mail tins of smokeless tobacco to smokers all over the country, such “diversion” (tracked by our team) has not been a problem. In the rare possibility that someone in the household takes an e-cigarette, either knowingly or unknowingly from study participants, this risk would be no greater than if that same individual took the participant’s cigarettes. The fact that we are using self-contained cartridges of e-cigarettes (NJoy), rather than refillable tank systems, minimizes the potential for adulterating the system by adding additional substances.

15.5 Confidentiality A final risk is breach of confidentiality.

Benefits: In an ever-changing marketplace of tobacco-products and nicotine-delivery devices, e-cigarettes are arguably the most popular new products available to smokers. The two most important questions about e-cigarettes are 1) uptake among non-smokers, and 2) impact among smokers. This study is poised to answer the latter, and is a strength upon existing research that is predominated by cross-sectional surveys and short term lab studies. There is a universal call for randomized trials of e-cigarettes, but these trials do not exist. It is important to test e-cigarettes before they become more popular, in advance of potential FDA role in regulation of them. E-cigarettes are classified as a tobacco product but in all likelihood will be subject to FDA regulation. The FDA will need high-level science to assess overall population impact. While this small pilot study alone will surely not address that need, it will certainly guide forthcoming research in this area.

This study is not without benefit to individual participants. However, this is not a treatment trial, and will not be advertised as such. We assess at screening for interest in cessation support. All comers will be accepted, but smokers actively seeking cessation support, or currently using cessation medication at baseline will be excluded. At all contacts, we will assess motivation to quit and uniformly offer referral information to state quitlines. Such transitions to cessation support are included as study outcomes. Two-thirds of the participants in the trial will receive samples of e-cigarettes, which most evidence to date suggests is a) safer than conventional cigarettes, and b) possibly related to quitting.

16. Collection, reporting and management of AEs and SAEs

Adverse events will be tracked and rated as mild, moderate or severe by the patient and rated as related to e-cigarettes by the research assistant using guidelines. We will determine if any adverse events result in dropouts or are serious according to FDA guidelines. A DSMB will assist in determining if the rate or severity of adverse events exceeds expectations.

The research staff will report any unexpected AEs or any scores of "severe" on the side-effect symptom rating form or any FDA-defined serious AEs to the PI within 24 hrs so that the PI can decide on the appropriate action. All unexpected AEs will be monitored while they are active to determine if treatment is needed. Since the e-cigarette sampling period is for a few weeks only, adverse events will be rare. Nonetheless, they will be coded on a weekly basis using the FDA's COSTART rules and entered into a database. For each weekly study meeting, the research assistants will prepare a summary of all AEs, including their severity, whether they occurred during smoking or abstinence, caused a dropout, required treatment and presumed relation to drug intake. The PI will review this at the weekly study meeting (or before if more urgent). At the weekly meeting (or before if urgent), research assistants will report any premonitory symptoms of emergence of a mental disorder such as depression or alcohol dependence. [name], a board-certified psychiatrist, and [name], a radiation oncologist, will be available for on-site medical supervision.

17. Plans for Interim Analyses of efficacy data

We plan to examine the data halfway through enrollment to determine if observed differences in quit rates are so large that the trial should be stopped early. Using the method of O'Brien and Fleming (143) the significance level for this interim analysis is $\alpha = 0.005$. According to this same reference, conducting this analysis decreases our power for detecting our projected differences only from 0.80 to 0.79.

18. Responsibility for data and safety monitoring

The PI will be responsible for monitoring the trial. The statistician will monthly examine the outcomes database for missing data, unexpected distributions or responses, and outliers. The PI will weekly check the AE database prepared by the research assistants immediately prior to the lab meeting a) to see if any particular COSTART categories are being endorsed more frequently than normal and b) to determine if any side-effect symptom checklist scores are higher than expected. A DSM report will be filed with the IRB and funding agency on a yearly basis, unless greater than expected problems occur. The report will include participant characteristics, retention and disposition of study participants, quality assurance issues and reports of AEs, significant/unexpected AEs and serious AEs. We will report efficacy at the end of the trial.

19. Frequency of DSM reviews

The DSMP will be reviewed annually.

20. Content of DSM report

The DSM report, which will be provided to all DSMB members, will include: a) enrollment data, in aggregate and split by gender and race, b) retention (% of all scheduled contacts that are completed), and c) adverse event data. Adverse event data will be presented in aggregate but will also include a detailed listing of all serious adverse events (SAEs).

